8.5.5.2 Serious Adverse Event Notification

The Clinical Supervisor notifies the Program Manager of all serious adverse events occurring in the program species on a quarterly basis, and the Program Manager is responsible for notifying all members of this program team.

8.5.6 Pregnancy

If pregnancy occurs in a participant or the female partner of a male participant in the 3 months after completion of the study, the investigator should fill out a pregnancy report form and report

it to the sponsor or the sponsor's designated representative and the Ethics Committee (if required) within 24 hours of being informed. Female participants should withdraw from the trial immediately after the occurrence of pregnancy.

Cases of pregnancy in the trial should be followed up with regard to the outcome of the pregnancy as well as the condition of the newborn to determine the outcome of the pregnancy (e.g., severe maternal complications, spontaneous or therapeutic abortion, ectopic pregnancy, stillbirth, neonatal death, congenital anomalies, or birth defects). In the case of live births, the newborn should be followed for up to **12 months** following the birth.

Although the pregnancy itself is not an SAE, complications or serious outcomes resulting from the pregnancy that meet the criteria for an SAE must be reported according to the procedures in [8.5.5](#). Elective abortion to terminate a pregnancy for no medical reason is not considered an AE/SAE.

8.5.7 Medication Error

Medication errors may result from the administration or consumption of the investigational product by the wrong participant, or at the wrong time, or at the wrong dosage strength, or noncompliance as described in Section [6.1](#) and [6.2](#).

Whether or not the medication error is accompanied by an AE, as determined by the investigator, the medication error is recorded on the medication error page of the eCRF and, if applicable, any associated AE(s), serious and nonserious, are recorded on an AE page of the eCRF.

If the associated adverse event fulfils serious criteria, the event should be reported to the Sponsor or delegate immediately (i.e., within 24 hours after learning of the event).

8.5.7.1 Treatment of Overdose

For this study, any dose of study intervention greater than that specified in the protocol will be considered an overdose. Sponsor does not recommend specific treatment for overdose.

Overdoses are medication errors that are not considered AEs unless there is an untoward medical occurrence resulting from the overdose.

In the event of an overdose or suspected overdose, the Investigator should:

1. Contact the Sponsor within 24 hours.
2. Closely monitor the participant for any AE/SAE.
3. Obtain a blood sample for PK/PD analysis if requested by the Sponsor (determined on a case-by-case basis).
4. Document the quantity of the excess dose as well as the duration of the overdose in the eCRF.

9 STATISTICAL CONSIDERATIONS

After the study protocol and CRF are completed and finalized, the development of statistical analysis plan will be carried out. The statistician will develop the relevant statistical analysis plan (SAP) according to the study protocol and the content of CRF, including the content of safety statistical analysis and PK, PD, etc. This is an exploratory phase 1 study with no statistical hypothesis by using descriptive statistical method, no additional assessments are needed. If there're protocol/CRF amendment or some additional analysis to be added during the course of study, the SAP will be revised if necessary. And any updates will be tracked with SAP version amendment after the initial SAP is finalized. The SAP will be approved by the sponsor before database locking. After database locking, the statistical analysis plan will not be modified in principle.

9.1 Sample Size Determination

This is an exploratory Phase I clinical study of the pharmacokinetics, pharmacodynamics, safety and tolerability of a single dose of Recombinant Human Thrombopoietin for Injection (rhTPO) in a single-center, single-arm, open-label, single-dose design in healthy volunteers from a Caucasian population. The sample size of this study is not based on statistical hypothesis and the study is planned to enrol approximately 22 healthy Caucasian participants.

9.2 Populations for Analyses

For purposes of analysis, the following populations are defined:

Table 8 Populations for Analysis

Analysis Set	Description
Safety analysis set (SS)	All participants enrolled and receiving the full dose of study drug and have at least one post-dose safety assessment. SS will be used for demographics, baseline characteristics, and safety analyses.
PK concentration set (PKCS)	All participants enrolled and receiving the full dose of study drug with at least one evaluable concentration data during the study. PKCS will be used for PK concentration analysis.
PK parameter sets (PKPS)	All participants enrolled and receiving the full dose of study drug with at least one evaluable PK parameter during the study. Participants whose PK parameter results affected by major protocol violations will be excluded from the PK parameter set. PKPS will be used for PK parameter analysis.
PD analysis set (PDS)	All participants enrolled and receiving the full dose of study drug with at least one evaluable PD data during the study, but participants whose PD e results affected by major protocol violations will be excluded. The PDS will be used for the pharmacodynamic analysis.
Immunogenicity Analysis Set (ADAS)	Participants with at least one immunogenicity result in the safety analysis set. ADAS will be used for immunogenicity analysis.

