4.3 Justification for Dose

In a single subcutaneous injection of rhTPO (0.25 µg/kg ~ 2.0 µg/kg) in Chinese healthy subjects conducted by the sponsor in 2001, a total of 27 subjects were enrolled in the study. The results showed that: only one subject's body temperature rose to 37.4°C 6 hours after the administration of rhTPO, and then fell back to normal 2 hours later; one subject experienced mild fatigue, poor appetite and drowsiness on the second day after the administration of rhTPO; no other uncomfortable reactions or abnormal signs were observed during the period of observation. In addition, in this study, 21 days after single subcutaneous administration of rhTPO, there were no significant changes in peripheral blood red blood cell and haemoglobin,

and no significant changes in white blood cell counts and classifications; platelet counts increased dose-dependently, and platelet counts increased gradually after administration of rhTPO, reaching a peak on the 10th to 14th day after administration of rhTPO. The PLT counts of the rhTPO 2.0 µg/kg group increased from $(209 \pm 40) \times 10^9/L$ to $(317 \pm 54) \times 10^9/L$ on 14th day after administration of rhTPO, and decreased to $(262 \pm 64) \times 10^9/L$ on 21st day after administration of rhTPO. There were no significant changes in mean platelet volume (MPV) and platelet distribution width (PDW) before and after the administration of rhTPO 2.0 µg/kg in the study.

In the single subcutaneous injection of rhTPO (300 U/kg) tolerance study in healthy Chinese subjects conducted in 2020, a total of 10 subjects were enrolled, and the results showed that: a total of 7 (70%) subjects experienced treatment emergent adverse event (TEAE), and all of the TEAEs were grade 1; 3 (30%) subjects experienced TEAE related to the investigational drug, and no medical intervention was given, and all of them recovered to normal by the completion date of the study. No serious adverse even (SAEs) and no TEAEs leading to withdrawal from the study occurred in this study.

Taken together, the above information suggests that rhTPO is expected to be safe for a single subcutaneous injection of 300U/kg (about 1.0 µg/kg) in healthy participants.

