5 STUDY POPULATION

5.1 Inclusion Criteria

Participants are eligible to be included in the study only if all of the following criteria apply:

1. Healthy **Caucasian** adult male and female participants aged 18-50 years (inclusive) at the time of informed consent. Caucasian is defined as of European, Middle Eastern, or North African descent.
2. Male participants weighing no less than 50 kg. Female participants should not weigh less than 45 kg.
3. Body mass index (BMI) within the range 18.0 to 32.0 kg/m² (inclusive).

Note: $BMI = \text{weight [kg]} / (\text{height [m]})^2$

4. Participants are in good general health as determined by the investigator, based on a medical evaluation including medical history, vital signs, physical examination, 12-lead electrocardiogram, clinical safety laboratory tests;
Note: Any results outside of the reference range at screening or baseline may be repeated once per the Investigator's discretion for the purpose of further determining eligibility.
5. Platelet counts must be within the normal range; measurements can repeat once for verification, if necessary.
6. Women of childbearing potential (WOCBP, see section 5.3.3) must have a negative serum or urine pregnancy test prior to the start of study drug and must not be breastfeeding, lactating or planning pregnancy during the study period. WOCBP who are not exclusively in same-sex relationships and males with partners of child-bearing potential must agree to use adequate contraception from signing the informed consent until 3 months after completion of the study. In addition, females must not donate ova (eggs) and males must not donate sperm from signing the informed consent until 3 months after completion of the study;
7. Negative for COVID-19 based on the nasopharyngeal or oropharyngeal swab with the method of real-time reverse transcription-polymerase chain reaction (RT-PCR) at Screening and Day-1.
8. Volunteer to participate in this study, be able to understand and comply with the clinical study protocol requirements, and sign the informed consent form in writing.

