6.1 Study Intervention(s) Administered

Table 6 Study drug

Generic Name	Recombinant Human Thrombopoietin for Injection (rhTPO)
Type	Drug
Dose Formulation	Lyophilized powder for injection
Unit Dose Strength(s)	15000 U/1mL/vial
Auxiliary materials	D(-)-Mannitol 40mg, α,α -trehalose dihydrate 20mg, polysorbate 20 (Tween 20) 0.05mg, sodium dihydrogen phosphate monohydrate 0.85mg, and di-sodium hydrogen phosphate dihydrate 0.6mg
Dosage Level(s)	300 U/kg
Route of Administration	Abdominal subcutaneous injection
Use	Experimental
Dosing Instructions	A single dose of 300U/kg will be administered through abdominal subcutaneous injection. For reconstitution, add 1.1 mL of sterile water for injection, sterile powder will quickly dissolve into a clear liquid. After reconstitution, this product can be stored at 2-8°C for 72

	h and at 20-25°C for 24 h (excursions may be permitted between 15-25°C), protected from light. It is recommended to use it as soon as possible upon reconstitution. Please refer to the Pharmacy Manual for details.
Storage conditions:	2~8°C, protect from light
China Marketing Authorization Approval number:	State Pharmaceutical Code S20050048
Sourcing	Shenyang Sunshine Pharmaceutical Co., Ltd.

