6.5 Study Intervention Compliance

Participants will be administered study drug in a controlled setting directly from the Investigator or designee, under medical supervision. All pertinent/required information on the preparation

and administration of the dose will be recorded in the source documents and recorded in the eCRF. The dose of study intervention and participant identification will be confirmed at the time of dosing by a member of the study site staff other than the person administering the study drug.

For additional information on study intervention compliance and management, refer to the Pharmacy Manual.

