9.3.4 Safety Analysis

The analysis of safety data (AE, TEAE, SAE, clinical laboratory parameters, ECG parameters, vital signs, and physical exam) will be descriptive and performed on the safety population. The adverse events incidence, overall and per CTCAE grade, will be presented. The attribution to the test drugs, time-of-onset, duration of the event, its resolution, and any concomitant medications administered will be reported.

Events will be reported on per-individual basis, i.e. counting individuals rather than events. This means that even if a patient suffers the same event repeatedly during the follow-up, the event will be counted only once. Repeated events in patients will be summarized according to the following rule: if a patient suffers the same event more than once, the event will be assigned the worst severity, the closest relationship to the drug and the earliest starting date. In the listings, however, all occurrences of the events will be shown.

All AEs reported will be classified using frequency and intensity, with the most recent version of the MedDRA and listed together with information on onset, duration, seriousness, expectedness, relationship, outcome, and countermeasures taken. Serious adverse events will be listed separately.

The absolute and relative frequencies of participants with any AEs will also be listed. Furthermore, the absolute and relative frequencies for participants with AEs will be provided by System Organ Class and Preferred Term according to the MedDRA. Similarly, degrees of intensity, causal relationship with the test drugs, and the countermeasures taken for each AEs will be tabulated for each treatment. The time of onset of AEs after treatment and their duration will be evaluated on a categorical basis.

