The Web-based Electronic Data Capture (EDC) Systems will be used to collect, store, and manage clinical data. The EDC database builder will establish the electronic case report form (eCRF) in EDC according to the protocol. Before EDC database goes live, the eCRF will be approved by Project Managers, Medical Reviewer and Biostatistician etc. The DM will conduct the EDC training and introduce the eCRF completion guideline for project managers, clinical research associates (CRA), investigators etc. After receiving the training, the relevant personnel can log into the EDC system and then enter the data into the eCRF. The EDC system can automatically verify the data in the eCRF and generate corresponding prompt messages. After the investigators modify and verify the entered data, the Principal Investigator or his/her authorized Investigators will sign electronically to confirm the data.

A 4.2 Data Review

The CRAs review the data entered into the eCRF by investigators for completeness and authenticity, and if necessary, query message to ask investigators to verify and revise until the data are accurate, complete and clean;

The data manager reviews the data entered into the eCRF by investigators for consistency and accuracy, and if necessary, query message to ask investigators to verify the changes until the data is accurate, complete and clean;

Medical reviewers to review eCRF data from medical expertise, if necessary, a query to ask investigators to verify modifications, until the data are accurate, complete, and clean;

All data issues should be confirmed before the database lock. The audit trails are required for all data changes and related operations.

A 4.3 Database Locking

If there is a data review meeting or other form of data review communication, the principal investigator, medical manager, project manager, data manager, and statistician should confirm any protocol deviation events that occurred in the trial and the impact on the statistical analysis dataset, and confirm that the database is complete and accurate before co-signing the relevant documents to lock the database. In principle, no further changes to the locked database are allowed. Problems found after data locking can be updated in the database or explained in the report after confirmation, and a written record will be kept. In order to ensure the security of the data, unrelated persons are not allowed to approach and modify the data, and the data must be backed up.

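### The safety analysis set requires the full dose, so a participant given only part of it is left out of the safety and immunogenicity summaries despite having been exposed

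*Protocol*

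**What the plan says.** Table 8 (Protocol, Section 9.2) defines the safety analysis set as "All participants enrolled and receiving the full dose of study drug and have at least one post-dose safety assessment". The same table assigns SS to demographics, baseline characteristics and safety analyses. Section 9.3.4 confirms that the safety analysis "will be descriptive and performed on the safety population".

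The immunogenicity set is nested in SS: "Participants with at least one immunogenicity result in the safety analysis set". The two PK sets (PKCS, PKPS) and the PD set (PDS) also require the full dose. The protocol gives no tolerance for what counts as full.

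Safety and tolerability, and immunogenicity, are secondary objectives (Section 3, Table 5).

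**The concern.** A safety population should contain everyone exposed to the drug. This one drops an exposed participant because of how much was given. Where an adverse reaction is the reason the injection was not completed, the exclusion is caused by the outcome being measured, and that reaction's incidence is understated. Where too little is given by mistake, and for laboratory, vital sign and ECG means, the bias could go either way.

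The protocol's own content makes partial exposure foreseeable, although no section mentions it directly:

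- Section 6.6.2 warns of anaphylactic reactions while the drug is being given as well as afterwards.
- Section 8.5.7 lists a wrong dosage strength among medication errors.

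This is not detail left to the SAP. The protocol fixes the definition, and Section 9 has the SAP written from the protocol, so an SAP that follows it repeats the exclusion.

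**Working it through.** The protocol states no figure to reproduce here. The check has three parts: set membership, the effect of one exclusion, and how a shortfall could arise.

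**1. Membership under Table 8.** Take a participant who received part of the dose, had a post-dose safety assessment and gave an ADA sample.

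| Set | Condition that decides | In the set? |
|---|---|---|
| SS | full dose | No |
| ADAS | membership of SS | No |
| PKCS, PKPS, PDS | full dose | No |

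No defined set contains this person, and no section readmits them.

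**2. Effect of one exclusion.** Inputs: about 22 participants (Section 9.1), and from the 2020 study of 10 healthy subjects, "3 (30%) subjects experienced TEAE related to the investigational drug" (Section 4.3). Assumption: exactly one of 22 exposed participants is partly dosed and is not replaced.

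- Reaction that stopped the injection, seen in nobody else:
  - all exposed: 1/22 = 4.5%
  - SS as written: 0/21 = 0%
- Related TEAEs at the 2020 rate: 0.30 × 22 = 6.6, taken as 7.
  - all exposed: 7/22 = 31.8%
  - SS, if the excluded participant had one: 6/21 = 28.6%, a shift of −3.2 percentage points
  - SS, if not: 7/21 = 33.3%, a shift of +1.5 percentage points

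If that participant withdrew and was replaced, as Section 7.1 allows at the discretion of sponsor and investigator, the first contrast becomes 0/22 = 0% against 1/23 = 4.3%. Replacement restores the size of SS but does not put the excluded person back.

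**3. How a shortfall could arise.** Inputs: 300 U/kg and a labelled strength of "15000 U/1mL/vial" (Section 6.1, Table 6), and the entry weights "Male participants weighing no less than 50 kg. Female participants should not weigh less than 45 kg" (Section 5.1).

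- Weight covered by one vial's labelled content: 15000 / 300 = 50 kg. Anyone heavier needs more than one vial.
- At 70 kg: 300 × 70 = 21000 U = 1.4 vials. One vial alone would be 15000/21000 = 71%.
- At 80 kg: 300 × 80 = 24000 U = 1.6 vials. One vial alone would be 15000/24000 = 62.5%.

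The 70 kg and 80 kg weights are illustrative. This part shows only that an incomplete dose is conceivable. It says nothing about how often, and the finding does not rest on it.

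**The case against.** The strongest reply is that the consequence is hypothetical. This is one supervised injection in a descriptive study without statistical tests. A second member of staff checks it: "The dose of study intervention and participant identification will be confirmed at the time of dosing" (Section 6.5). Two team members document dispensing and administration (Section 6.2). If everyone is fully dosed, the wording changes no result.

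Nor would the data be lost. Section 8.5.7 has every medication error recorded in the eCRF, with any associated AE on an AE page. AE recording, SAE reporting and the stopping rule (Sections 8.5.3, 8.5.5.1 and 5.6) do not depend on SS. Section 9.3.4 can be read as listing every reported AE. A data review, if one is held, would "confirm any protocol deviation events that occurred in the trial and the impact on the statistical analysis dataset" (Section 10, A 4.3). Needing more than one vial is ordinary weight-based preparation, and a tolerance for full dose could be set in the SAP or the Pharmacy Manual.

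Most of this stands as a limit on size: the case is probably rare, and what is at risk is the summary tables and their denominators, not the capture of events. It does not rescue the definition. None of these safeguards returns the participant to SS or ADAS. Readmission at data review would mean departing from the written rule once the data are known, in an open-label study.

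A further objection is that the requirement for a post-dose safety assessment can also remove exposed participants. That is true in principle. However, injection-site assessment is scheduled from 0.5 h after dosing (Section 1.3, Table 1), while participants are on the ward, so that condition should rarely bite.

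**Conclusion.** The concern holds. Followed as written, Table 8 removes an exposed participant from the planned safety and immunogenicity summaries. When a reaction stopped the injection, the incidence of that reaction is understated: 0% instead of 4.5% with one such participant among 22. For related TEAEs at the 2020 rate, one exclusion moves the estimate by −3.2 or +1.5 percentage points, depending on whether that participant had an event.

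These figures assume one partly dosed participant. The protocol gives no rate of incomplete dosing, and none is assumed here. The primary PK analysis is unaffected, and the full-dose condition is reasonable for the PK and PD sets. The definition should be corrected: it is wrong in principle, even though the practical effect is likely to be small.

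**What to change.** In the SS row of Table 8, replace the full-dose condition with receipt of any amount of study drug. Leave the post-dose assessment condition as it is. ADAS then follows without further change. Keep the full-dose condition for PKCS, PKPS and PDS. How a partly dosed participant is identified in tables and listings can be left to the SAP.

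A minor, separate wording point can be settled in the same amendment. Section 9.3.2 bases participant disposition on SS but asks for screened and screen-failed counts, which SS cannot supply. Base disposition on all screened and all enrolled participants.

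The cost is one phrase in Table 8 and one sentence in Section 9.3.2, with no change to data collection, visits or sample size.

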9.3 Statistical Analyses

This section is a summary of the planned statistical analyses of the most important endpoints including primary and secondary endpoints.

There is no statistical hypothesis associated with the study objectives. As such, no statistical tests will be performed. The analyses of safety, efficacy, biomarker and pre-defined subgroups will primarily be descriptive.

